1.5 Treatment-Emergent Adverse Events

A treatment-emerging adverse event is defined as

- an undesirable sign, symptom, or medical condition with onset after the first dose of study medication or,
- an increase in severity of an event that is present during the pre-treatment period,
- all events included on the database will be included in AE summary tables/listings.

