2.1.6 Study medication

The study consists of three treatment periods.

In Period 1 patients will be randomized to metformin + vildagliptin 50mg bid, or metformin + placebo. If initial treatment fails to maintain HbA1c < 7.0%, confirmed at two consecutive scheduled study visits (after remapping in [section 1.3.3](#) has been applied), starting from Visit 4 (Week 13), then vildagliptin will be added to metformin in the metformin-only arm in Period 2. The Period 1 end date is defined as the date of the second of the two consecutive scheduled study visits, i.e. the initial treatment failure date. The Period 2 start date is defined as the next day.

In Period 3, insulin is considered based on local guidelines. Both patients and investigators will remain masked to the treatment allocation in Period 1, and the study will compare the two different treatment approaches. The Period 3 start date is defined as the date of insulin initiation. The Period 2 end date is defined as the previous day.

Treatments are referred to as ‘Treatment approach’ throughout this analysis plan to acknowledge that patients are not on the same treatment for the duration of the study. When summaries are detailed for the ‘Treatment Period’, they will include data from Periods 1, 2 and 3, unless specified otherwise.

The duration of exposure to study medication (in months) during the treatment period will be computed for all patients using the algorithm outlined in [Section 1.4](#) and summarized by treatment approach for the RAN both descriptively (i.e., mean, standard deviation, median, minimum and maximum) and by 3 - monthly intervals (0 - < 3 months, 3 - < 6 months, ..., ≥ 60 months).

The study Period 1 duration (in months) will be also similarly summarized for the RAN. The study Period 1 duration is defined as (initial treatment failure date – treatment start date + 1)/30.4375 for patients who entered study Period 2. The study Period 1 duration is the same as overall study duration for patients who did not enter into Period 2.

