2.3 Safety evaluation

The safety and tolerability of vildagliptin 50mg bid as add-on to metformin over 5-years of treatment will be compared to placebo as add-on to metformin based on data collected during the treatment period in SAF. All analyses will use all available data collected during the entire study. In addition, key safety analyses will be performed on data obtained during Period 1 only. Patients will be analyzed according to the treatment approach they received (vildagliptin 50mg bid + metformin, placebo + metformin).

The incidence of treatment emergent adverse events (events started after the first dose of randomized study medication or events present prior to start of randomized treatment but increased in severity) will be summarized by primary system organ class, preferred term, severity and relationship to study drug. Any event captured on the database will be included in AE summary tables/listings.

In order to assess safety and tolerability of vildagliptin as compared to placebo, key safety variables (overall AEs, SAEs, AEs leading to study drug discontinuation or study drug interruption, incidence of hypoglycemia, predefined AE risks, predefined categories of liver enzyme (ALT/AST) and CPK and persistent elevations) will also be summarized by treatment approach for the SAF.

The number and percentage of run-in failures reporting any adverse events, serious adverse events or adverse events leading to study drug discontinuation will also be summarized. Note

these events will not be included in other AE outputs, as these patients will not be included in SAF.

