2.3.1 Overall experience of adverse events (AEs)

The number and percentage of patients reporting any adverse event during the treatment period of the study will be summarized by primary system organ class, preferred term and treatment approach overall (including study periods 1, 2 and 3) and by study period. Percentages will be based on the number of patients in the SAF per treatment approach and study period. An AE will be assigned to a period if its start date is after or on the start date but not later than the end date of that period. All AEs will be assigned to a specific study period – if it is not possible to assign an AE into a specific study period of the patient based on the AE start date, then the event will be assigned to the last study period started by the patient. This will ensure that all AEs will be categorized to a specific study period

The most common adverse events reported ($\geq 2\%$ in any group) during the treatment period of the study will be presented in descending frequency starting from the most common event in a Text Table. A complete table of all events reported in descending frequency will be prepared..

Adverse events that were suspected to be related to study drug will be summarized. Note that if the relationship to study drug is missing for any adverse event, then that adverse event will be assumed to be related to study drug.

The maximum severity of all adverse events during the treatment period of the study will be summarized. Note that if the severity is missing for any adverse event, then that adverse event will be assumed to be severe.

An overall summary of the number and percentage of patients with drug-related AEs, severe AEs, AEs with outcome of death, SAEs and adverse events leading to permanent discontinuation of treatment will be presented by study period and treatment approach.

The number and percentage of patients reporting any adverse event during the treatment period of the study will be summarized by standardized MedDRA query (SMQ) level and treatment approach as well.

In addition, the number and percentage of patients reporting any adverse event during the treatment period will also be summarized by primary system organ class, preferred term, treatment approach and age group (as defined in section 2.1.5)) overall and by treatment period..

Note that there will be no AE adjudication for this study.

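### SAP Addendum 1 is inconsistent on whether AEs before the first randomised dose enter the AE tables and, read literally, may file them under a later study period

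*SAP*

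**What the plan says.** Text that keeps pre-dose events out:

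- SAP Addendum 1, 2.3 describes the summarised events as those starting after the first randomised dose, together with "events present prior to start of randomized treatment but increased in severity".
- SAP 2.3.1 tabulates AEs of the treatment period. For summaries of that period, SAP 2.1.6 says "they will include data from Periods 1, 2 and 3, unless specified otherwise".

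Text that brings them in:

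- The next sentence of SAP 2.3 reads "Any event captured on the database will be included in AE summary tables/listings".
- SAP 1.5 has the same rule as a bullet inside the definition of a treatment-emergent event: "all events included on the database will be included in AE summary tables/listings". Its onset bullet refers to study medication without the word randomized.

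Period rule, SAP 2.3.1: "An AE will be assigned to a period if its start date is after or on the start date" and no later than the end of that period. Every AE is to receive a period. If the start date cannot place the event, "then the event will be assigned to the last study period started by the patient".

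Run-in events are on the database. Protocol Table 6-1 marks AEs from Visit 2 (week -3), and protocol 6.1 and 7.1 start AE reporting at informed consent. SAP 2.3 plans a separate summary of "The number and percentage of run-in failures reporting any adverse events, serious adverse events or adverse events leading to study drug discontinuation". Those patients are kept out of the other AE outputs because they are not in the safety set. Nothing similar is said about run-in events of patients who go on to be randomised.

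**The concern.** Two programmers following this SAP could build different AE tables. One would drop a run-in event that did not worsen. The other would count it as on-treatment and, finding no period that contains its start date, place it in the last period the patient reached.

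Such events are foreseeable. The run-in starts or up-titrates metformin, and protocol 3.1.1 and 3.2 plan for gastrointestinal side effects in it. Under protocol 5.2, placebo-arm patients take vildagliptin plus metformin in Periods 2 and 3. A run-in event of such a patient could therefore appear in a column for a treatment not yet begun when the event occurred. What is at stake is the accuracy of the safety tables, above all the by-period tables of SAP 2.3.1, 2.3.1.1 and 2.3.5.

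**Working it through.** The plan gives no figure on this point to reproduce, so the check is mainly a comparison of texts.

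**Step 1. One event, each rule.** Take a randomised, dosed patient with a run-in AE that has a known start date and does not worsen.

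| Text (SAP Addendum 1) | Result |
|---|---|
| 2.3, treatment-emergent definition | Not summarised |
| 2.3.1 with 2.1.6, treatment period | Not summarised |
| 1.5, onset bullet | Depends on whether run-in metformin is study medication |
| 1.5 and 2.3, events on the database | Goes into tables/listings |
| 2.3.1, period rule and fallback | Must have a period; goes to the last one started |

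The third row is open because the protocol glossary counts metformin as study drug and protocol 5.5.4 dispenses it as such at Visit 2. By the wording of 1.5 alone, an event after the first run-in tablet could be called treatment-emergent.

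**Step 2. Where Period 1 begins.** SAP 2.1.6 dates the end of Period 1, the start and end of Period 2 and the start of Period 3. It does not date the start of Period 1. Its Period 1 duration is counted from the treatment start date, which SAP 1.4 sets at the earliest vildagliptin/placebo date. A run-in event therefore lies before every period.

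**Step 3. The period rule applied literally.** Assume, for illustration only, Period 1 on days 1-365, Period 2 on days 366-900 and Period 3 on days 901-1820.

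- Onset on day 20: Period 1.
- Onset on day 1840: no period fits, so the fallback gives Period 3. This is a sensible use of the rule.
- Onset on day -10: no period fits, so the fallback also gives Period 3, although the event came before any randomised dose.

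**Step 4. Size of the window.** AEs are collected from Visit 2 at the latest. Visit 3 follows within 3 weeks, and planned treatment runs to week 260. For a completer the pre-dose share of observed time is at most

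3 / (3 + 260) = 3/263 = 1.1%.

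Patients who enter on 1000 to 2000 mg metformin daily go straight to randomisation (protocol 3.1.1) and have no run-in. Collection from consent was introduced by Amendment 3. The documents do not say how many patients were screened under it, so the earlier screening weeks are not counted here. The 1.1% is a share of time, not of events. The documents give no pre-dose AE rate, so the number of events cannot be estimated.

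**The case against.** The strongest reply is that SAP 2.3.1 can be read consistently. Its paragraph opens with AEs of the treatment period, so the instruction to give every AE a period, and the fallback, may apply only within that scope. The fallback would then serve missing or partial dates and onset after the last period. It never mentions the run-in. This reading is fair, and it is why the misfiling is only what the literal text allows. It does not remove the conflict inside SAP 2.3, where the treatment-emergent definition and the database sentence stand next to each other. A listing alone could satisfy the phrase tables/listings, but the SAP does not say so. By contrast, SAP 2.3.2 states outright that only treatment-emergent notable laboratory abnormalities count.

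A reader might infer four stronger points that the documents do not support:

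- That "All analyses will use all available data collected during the entire study" also brings run-in events in. In SAP 2.3, as in protocol 9.5.3, that statement is set against analyses of Period 1 only. It contrasts the whole study with Period 1 and does not address pre-dose events.
- That a pre-dose event which worsens always goes to the last period. Protocol 7.1 defines an AE as an appearance or a worsening and asks for its start date. A worsening recorded in that way has its own date, and the period rule works.
- That the hypoglycaemia window is 5 weeks, giving 5/(5 + 260) = 1.9%. Protocol 6.1 does refer to Visit 1 to Visit 3. But protocol 6.5.6 issues the meter and diary at Visit 2, or at Visit 3 for patients without a run-in, and SAP 2.3.5 counts diary entries. The practical window is again up to 3 weeks.
- That the comparison between arms is biased. Pre-dose events arise before randomised treatment can act, and the documents give no rate from which to derive an effect on the by-period tables.

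**Conclusion.** The inconsistency is real and minor. SAP 1.5 and 2.3 give opposite instructions for a non-worsening AE of a randomised patient that starts before the first vildagliptin/placebo dose. On the literal reading of 2.3.1, that event is counted as on-treatment and may be filed in Period 2 or 3.

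The exposed window is up to 3 weeks, about 1.1% of a completer's observed time, and the number of events is unknown. The conclusion assumes that run-in AEs of randomised patients are on the database, which protocol Table 6-1 supports, and that Period 1 starts at the first randomised dose, which the SAP implies. The primary endpoint and arm assignment are unaffected, and no between-arm bias is claimed. Run-in failures are outside the point, because SAP 2.3 handles them separately.

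**What to change.** 1. In SAP 1.5 and 2.3, limit AE summary tables to events with onset on or after, or worsening after, the first dose of randomised medication (vildagliptin/placebo). Use that same term in both sections. Confine the database sentences to listings, and list pre-dose events of randomised patients separately.
2. In SAP 2.3.1, state that Period 1 starts on the treatment start date of SAP 1.4. State also that events with known onset before that date are not eligible for the last-period fallback. Keep the fallback for unusable dates and for onset after the last period.
3. Where the worsening of a pre-dose event is recorded as an AE under protocol 7.1, assign it by the start date of the worsening.
4. Apply the same rules to the by-period hypoglycaemia summaries in SAP 2.3.5.

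The rule for missing or partial dates needs no change. The cost is a few sentences of SAP text and one date filter, since onset and first-dose dates are already collected. The downside is that some AE percentages fall slightly and run-in events move from the tables to a listing.

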2.3.1.1 Deaths, other serious and other significant adverse events

An overall summary of the number and percentage of deaths, serious adverse events (SAEs), and adverse events (including laboratory abnormalities) leading to discontinuation, study drug interruption or considered to be clinically significant will be presented by study period and treatment approach.

Deaths

The number and percentage of deaths will be summarized by study period and treatment approach and the principal cause in primary system organ class and preferred term.

Serious adverse events (SAEs)

The number and percentage of patients with serious adverse events (SAEs) will be summarized by primary system organ class, preferred term, study period and treatment approach.

Other significant adverse events – adverse events leading to discontinuations

The number and percentage of patients with adverse events that lead to discontinuation will be summarized by primary system organ class, preferred term, study period, and treatment approach.

Other significant adverse events – adverse events leading to dose adjustments or study drug interruptions

The number and percentage of patients with adverse events that lead to dose adjustments or study drug interruptions will be summarized by primary system organ class, preferred term, study period, and treatment approach.

Other significant adverse events – predefined adverse event risks

The number and percentage of patients with adverse events that were predefined risks (see [Section 1.6](#) for definitions) will be summarized by preferred term, predefined risk category, maximum severity, study period, and treatment approach.

2.3.2 Laboratory values

The details of laboratory parameters collected, SI units (note, only SI units will be reported), and normal ranges will be listed in [Section 16 of CSR](#). Note that lipid parameters are summarized along with other biochemistry laboratory parameters. Meal test laboratory parameters (glucose, insulin and c-peptide) are for use in efficacy analyses only and so should not be included in safety laboratory outputs.

Notable ranges (absolute) criteria of selected laboratory variables are defined in [Section 1.8](#) above. The laboratory values to be considered for notable ranges or relevant changes will include all post-baseline values up to the final scheduled visit, including values at unscheduled visits prior to the last visit. Only treatment emergent notable abnormalities will be considered (i.e. notably abnormal measurements which were not present at any pre-baseline visit). In addition to summary tables, a listing of patients with any treatment emergent notable laboratory results during the treatment period will be provided by treatment approach and patient number, along with their values at all visits, including repeated, unscheduled and follow-up laboratory values. In the listing, all abnormal values outside of normal range and notable values will be flagged, e.g., L/H for a value being below/above normal range, LN/HN for a value being in notable low/high range.

For each numerical laboratory parameter, the laboratory values will be reported in listings to the same precision as that for the unit in UNITCONV dataset. The precision to use in tables is as per [Section 1.3.1](#).

For continuous variables with a value <lower limit, these will be imputed as being half of the lower limit. For continuous variables with a value >upper limit, these will be imputed as being equal to the upper limit.

2.3.2.1 Hematology

The values of hematology laboratory test results at baseline and endpoints (End of Period 1, End of Period 2, End of Study) will be summarized, as well as the changes from baseline to each endpoint.

The maximum/minimum value obtained during the treatment period, and the change from baseline to maximum/minimum value will be summarized by treatment approach for each hematology parameter.

The number and percentage of patients with abnormal hematology test results meeting notable criteria post-baseline, which were not present prior to randomization, will be tabulated. This summary will be repeated for abnormalities occurring in Period 1.

2.3.2.2 Biochemistry

The values of biochemistry laboratory test results at baseline and endpoints (End of Period 1, End of Period 2, End of Study) will be summarized, as well as the changes from baseline to each endpoint.

The maximum/minimum value obtained during the treatment period, and the change from baseline to maximum/minimum value will be summarized by treatment approach for each hematology parameter.

The number and percentage of patients with abnormal biochemistry test results meeting notable criteria post-baseline, which were not present prior to randomization, will be tabulated. This summary will be repeated for abnormalities occurring in Period 1.

The number and percentage of patients with hepatic enzyme elevations (defined in [Table 1-3](#)), and persistent hepatic enzyme elevations will be presented, and the patients meeting any of the criteria will be listed. Note that for this study total bilirubin will be used for all criteria involving bilirubin. If at any visit total bilirubin has not been measured then the elevation will not be assessed for that visit (even if direct bilirubin has been measured).

The liver panel A testing data for patients with hepatic enzyme elevations will be listed at patient level. Liver panel B testing data will not be considered as part of the RAP, but will be included in narratives if applicable.

2.3.2.3 Urinalysis

The baseline and endpoints (End of Period 1, End of Period 2, End of Study) values of categorical urinalysis test results will be summarized in number and percentage by treatment approach. The baseline and endpoints (End of Period 1, End of Period 2, End of Study)

values of continuous urinalysis test results will be summarized by treatment approach using descriptive statistics.

2.3.3 Vital signs

Baseline and endpoint values for blood pressure (sitting), and pulse (sitting) will be presented. Summary statistics for vital signs data will be presented by study visit. The summary by study visit will include only values obtained at the scheduled visit.

The number of patients with notably abnormal vital signs [REDACTED] post-baseline will be presented. This summary will be repeated for abnormalities occurring in Period 1. The criteria for notable abnormalities (see [Section 1.9](#)) will be listed.

2.3.4 Electrocardiograms (ECGs)

Overall interpretation and details of abnormalities are collected at Screening and selected visits.

Change from the baseline ECG result to the endpoint (End of Period 1, End of Period 2, End of Study) ECG result will be summarized by a shift table. The number of patients with clinically significant abnormalities or not at baseline and at each endpoint ECG assessment will be tabulated.

2.3.5 Hypoglycemic events

Hypoglycemic events will be characterized by event profile, such as ability to self-treat, self monitoring of plasma glucose level, precipitating event, time from last meal, time from last dose, and time of the day.

The incidence of hypoglycemic events (coded as hypoglycemia) and asymptomatic low blood glucose (coded as Blood Glucose Decreased), entered into the Glycemia study diary eCRF and meeting the event criteria defined in [Table 1-1 \(Section 1.7\)](#), are included in all of the AE summaries in [Section 2.3.1](#).

In addition, patients reporting at least one hypoglycemic event, the subgroup of reporting 1 event, 2 events, and >2 events, patients discontinued due to hypoglycemic events, patients reporting grade 2 events, and patients reporting suspected grade 2 events will be summarized by numbers and percentages for each treatment approach overall (including study periods 1, 2 and 3) and by study period. The summary will be repeated by age group (as defined in [section 2.1.5](#)).

The hypoglycemic events will further be summarized by event profile as follows:

- plasma glucose level ≤ 2.2 , $>2.2-\leq 2.8$, $>2.8-\leq 3.1$ and ≥ 3.1 mmol/L, or Not recorded; note that if a patient is unable to initiate self-treatment and plasma glucose is not recorded, this is graded as a suspected grade 2 event)
- grade (grade 1, grade 2 or suspected grade 2)
- symptom (in preferred term)
- precipitating event (None, Missed/delayed meal, Strenuous exercise, Alcohol consumption, Other or Not recorded)

- severity (Mild, Moderate, Severe)
- relationship to study drug (Not suspected, Suspected)
- action taken (Study drug dosage adjusted / temporarily discontinued, Study drug permanently discontinued, Concomitant medication taken, Non-drug therapy given (includes oral carbohydrates), Hospitalization / prolonged hospitalization, no action taken)
- time interval between last meal and event (0–4, >4–6, >6 hours, not recorded),
- time interval between last dose and event (0–4, >4–6, >6 hours, not recorded),
- time of the day in 24-hour clock (>00:00–06:00, >06:00–12:00, >12:00–18:00, or >18:00–24:00),

[figure not shown]
Asymptomatic blood glucose events will be similarly summarized by event profile and the number of patients with at least one asymptomatic low blood glucose measurement will also be summarized.

[figure not shown]
A listing of hypoglycemic events and asymptomatic low blood glucose events will be presented by treatment approach and patient number.

[figure not shown]
Note: As defined in [Table 1-1](#), for patients who are able to initiate self-treatment (where necessary) symptoms suggestive of hypoglycemia which are not confirmed by glucose measurements will be recorded in the Glycemia diary eCRF. Since these are not confirmed hypoglycemia events, these symptoms will not be reported in the hypoglycemia summary tables and listings, these symptoms will appear only in the AE tables and listings. For patients unable to initiate self-treatment (where necessary) symptoms suggestive of hypoglycemia that were not confirmed by glucose measurements will be classed as suspected hypoglycemic events and will therefore be reported in the hypoglycemia summary tables and listings, as well as the AE listings.

[figure not shown]
Note: Self-monitoring glucose can be recorded in the database as either plasma or whole blood. However, only plasma glucose will be reported in the tables and listings. Thus blood glucose values will be converted into plasma glucose equivalent, which can be done by multiplying a conversion factor of 1.12, i.e., plasma glucose = blood glucose × 1.12.

The incidence of hypoglycemia and severe hypoglycemia during Period 1 will be compared for the SAF using a chi-square test between the two treatment approaches for all patients provided that the incidence such these events is more than 5 in each treatment approach.

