6.5 Safety

- Physical examination.
- Vital signs.
- [REDACTED]
- Monitoring of hematology, blood chemistry and urine tests.
- LFT.
- ECG.
- Pregnancy (see [Section 6.5.8](#) & [Section 7.3](#)).
- Incidence of hypoglycemia events.
- All treatment emergent AEs/SAEs (see [Section 7](#)).

■ [REDACTED]

The endpoints for the safety objective include treatment emergent AEs (including hypoglycemia events), SAEs, laboratory test results and vital signs.

Incidence of confirmed hypoglycemic events, of all symptomatic episodes and of severe hypoglycemia (defined as an event requiring assistance from another person and associated with either self-monitoring blood glucose ≤ 3.1 mM (≤ 56 mg/dL), see [Table 6-5](#)).

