3	06May2019	
Section 1.4 Changed duration derivation from weeks to Months.
 
Section 1.6 Added the list of AEs of special interest
 
Section 2.1.2 Added information of efficacy parameters to be considered for deviation code N02 and N03.
 
Section 2.1.5 Removed definition of baseline HbA1c and FPG as it was redundant. Baseline is already defined in section 1.1
 
Section 2.1.5 redefined age classification based on tertiles
 
Section 2.1.6 redefined exposure categories in months instead of weeks.
 
Section 2.2.1 Added table mentioning grouping for geographical regions
 
Section 2.2.2 Removed loss of glycemc control as primary endpoint; provided additional detail to used confirmation visit for time to initial treatment failure; Since we have only one primary endpoint, removed multiple testing methods section
 
Section 2.2.2.4 Added time to first treatment failure as supportive analysis; modified age categories for subgroup analysis; added smoking status, region and beta cell functional and insulin resistance as subgroups of interest; removed ethnicity
 
Section 2.2.3 Added rate of glycemc control over time as secondary endpoint; [REDACTED]

[figure not shown]
Version	Date	
		
analyzed and it is outside the scope of the SAP
 
Section 2.2.3.3 Added the analysis of rate of glycemic control over time in this section
 
Section 2.3.5 Added clarification on using chi square test to compare events only if we have sufficient observed events.
 
Section 2.7 Updated power calculations based on single primary endpoint and updated yearly dropout rate.

Addendum 1	17Dec2019	
Section 2.2.2.4 Time to second treatment failure endpoint is added as a post-hoc analysis
 
Section 2.2.2.4 Subgroup analysis for the primary endpoint is added as a post-hoc analysis.
 
Section 2.7 Updated sample size section based on the protocol amendment 4

Table of contents

Clinical Development	1
List of abbreviations	6
1 Definitions and general strategy	7
1.1 Baseline definitions	7
1.2 Last On-Treatment Observation (Endpoint Observation)	7
1.3 General data handling strategy	8
1.3.1 Output data precision	8
1.3.2 Efficacy Assessment Window / Week X Measurement	8
1.3.3 Laboratory visit windows.....	9
1.3.4 Multiple laboratory measurements within same day	10
1.4 Duration of exposure to study medication.....	10
1.5 Treatment-Emergent Adverse Events	10

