1.6 Other clinically significant events (predefined AE risks)

For this project, there are some predefined adverse event risks that are considered of special interest defined as below:

Important identified risks

- Transaminase elevations and Drug-induced liver injury (DILI)
- Angioedema

- Acute pancreatitis
- Skin lesions (pemphigoids)
- Hypoglycemia
- Lactic acidosis (metformin)

Important potential risks

- Serious infections
- Cardiac events in CHF (NYHA Functional Class III) patients (adjudication)
- Muscle events/ myopathy/rhabdomyolysis
- Neuropsychiatric events
- Breast cancer
- Pancreatic cancer

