1.7 Hypoglycemic Event Classifications

Patients were educated to record hypoglycemic symptoms and treatment in a study diary. Study diary data were then entered in the Glycemia Study Diary or Adverse Event eCRF, respectively according to the following criteria. The Glycemia study diaries were reviewed by the study staff at each visit and assessed according to [Table 1-1](#). Note that if glucose is recorded as whole blood on the eCRF, rather than plasma, then it will be converted to a plasma value in the derived dataset, using a conversion factor of 1.12 (i.e. plasma glucose = blood glucose x 1.12).

Table 1-1 Recording and classification of glycemia study diary data

Severity	Symptoms	Plasma glucose	Action taken	Classification
Patient able to initiate self-treatment if necessary	Symptoms suggestive of hypoglycemia	< 3.1mmol/L (56mg/dL)	Enter in Glycemia Study Diary eCRF	Hypoglycemic event, grade 1
	Symptoms suggestive of hypoglycemia	≥ 3.1mmol/L(56mg /dL)	Enter in Glycemia Study Diary eCRF	Adverse Event
	Symptoms suggestive of hypoglycemia	Not taken	Enter in Glycemia Study Diary eCRF	Adverse Event
	Asymptomatic	< 3.1mmol/L(56mg /dL)	Enter in Glycemia Study Diary eCRF	Asymptomatic low blood glucose
Patient is unable to initiate self-treatment and requires assistance of another person or hospitalization	Symptoms suggestive of hypoglycemia	< 3.1mmol/L(56mg /dL)	Enter in Glycemia Study Diary eCRF & report as SAE	Hypoglycemic event, grade 2 & SAE
	Symptoms suggestive of hypoglycemia	Not taken	Enter in Glycemia Study Diary eCRF & report as SAE	Suspected hypoglycemic event, grade 2 & SAE

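### The Period 1 hypoglycemia chi-square is skipped whenever either arm has 5 or fewer, and no fallback test is named

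*SAP*

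**What the plan says.** The last paragraph of SAP section 2.3.5, in the same words in V3.0 and Addendum 1, plans a chi-square test in the safety set for two Period 1 outcomes, hypoglycemia and severe hypoglycemia. The test is run "provided that the incidence such these events is more than 5 in each treatment approach". The SAP document history, under version 3, explains the condition: "Added clarification on using chi square test to compare events only if we have sufficient observed events". Neither document names another test. Protocol section 9.5.3 plans summaries of hypoglycemia and no between-arm test, so the test is an SAP addition. The descriptive output does not depend on the condition: patients with events "will be summarized by numbers and percentages for each treatment approach", overall and by study period. SAP section 1.6 lists hypoglycemia under "Important identified risks".

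For the second outcome, section 2.3.5 does not say what counts as severe. It lists "grade (grade 1, grade 2 or suspected grade 2") and, separately, "severity (Mild, Moderate, Severe"). Protocol section 6.5 speaks "of severe hypoglycemia (defined as an event requiring assistance from another person and associated with either self-monitoring blood glucose" at or below 3.1 mM, with a reference to Table 6-5. In SAP Table 1-1, an event needing assistance with no glucose reading is a "Suspected hypoglycemic event, grade 2 & SAE".

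**The concern.** The usual condition for a chi-square test on a 2x2 table is that the expected cell counts are large enough, commonly at least 5. With equal arms, the expected number with an event is the same in both and equals half the total. A rule on the observed count in each arm is different: it fails whenever one arm is low, however high the other is. The test is then missing in the tables where a between-arm difference is clearest. Fisher's exact test would cover sparse tables, so sparse data alone do not require leaving the comparison out.

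What is at stake is limited: one between-arm p-value per outcome, for a risk the sponsor itself lists. The outcome labelled severe is the rarer one and so the likelier to fall under the threshold. Its content could also differ between two programmers reading the same text.

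**Working it through.** **Inputs.** The planned size is 1000 per arm (SAP 2.7), used for the safety set because its size is not given. The documents state no hypoglycemia rates, alpha or sidedness for this test. Assumed: two-sided 0.05, chi-square without continuity correction, a range of true rates, and the 5 read as patients with an event, since a 2x2 test needs patients. There is no plan figure to reproduce.

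**Single tables.** With a and b patients with an event and n = 1000 per arm, the expected count in each arm is (a + b)/2, and

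chi-square = 2n[a(n − b) − b(n − a)]² / [(a + b)(2n − a − b)n²].

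- 0 against 12: expected 6 and 6. Chi-square = 2000 × 12,000² / (12 × 1988 × 10⁶) = 12.07, p=0.0005; Fisher p=0.0005. Not tested.
- 5 against 20: expected 12.5 each. Chi-square = 2000 × 15,000² / (25 × 1975 × 10⁶) = 9.11, p=0.0025; Fisher p=0.0039. Not tested.
- 6 against 7: expected 6.5 each. Chi-square = 2000 × 1000² / (13 × 1987 × 10⁶) = 0.08, p=0.78. Tested.

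With both arms at 5 or fewer, the smallest Fisher p is 0.062 (0 against 5), so nothing is lost there. With 0, 1, 2, 3, 4 or 5 in the lower arm, Fisher reaches p<0.05 once the other arm has 6, 8, 10, 12, 13 or 15. These limits are the same at 900 per arm.

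**Chance of a significant result.** All 2x2 tables are enumerated with binomial probabilities. The condition is met with probability P(X₁ > 5) × P(X₂ > 5). The alternative rule is chi-square if all expected counts are at least 5, and Fisher otherwise.

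| True rates | Condition met | Significant, as written | Significant, alternative rule |
|---|---|---|---|
| 0.2% vs 0.4% | 0.4% | 0% | 5% |
| 0.3% vs 0.6% | 4.6% | 0% | 11% |
| 0.5% vs 1.0% | 36% | 1.6% | 24% |
| 1.0% vs 2.0% | 93% | 40% | 46% |
| 2.0% vs 4.0% | 100% | 76% | 76% |
| 0.3% vs 0.9% | 7.4% | 0.2% | 38% |
| 0.5% vs 1.5% | 38% | 14% | 64% |
| 0.5% vs 2.0% | 38% | 29% | 89% |
| 1.0% vs 3.0% | 93% | 85% | 91% |

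**Other readings of the 5.** If it counts events and patients may have several, the condition is met more often. This was simulated with 400,000 trials, geometric events per affected patient, the condition on events and the test on patients. At 0.5% against 2.0%, the as-written figure rises from 29% to 56% (assumed mean 1.5 events per affected patient) or 68% (mean 2), still against 89%. At 0.5% against 1.0%, it rises from 1.6% to 8% or 12%, against 24%. If the 5 is a percentage, the condition is stricter: more than 5% of 1000 is more than 50 patients in each arm.

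**Severe hypoglycemia.** The protocol 6.5 wording ties a severe event to a glucose value. A suspected grade 2 event has none, so it cannot meet that wording, yet it is reported as grade 2 and as an SAE. Protocol 6.5 also uses at or below 3.1 mM, where both classification tables use below 3.1.

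**The case against.** The strongest reply is that the condition is deliberate. The document history shows a decision to test only with enough data, and below the threshold the plan is descriptive. No alpha, hypothesis or decision is attached to the p-value, so the power figures rest on a level supplied here. Protocol sections 3.4 and 3.6 expect very little hypoglycemia in either arm, and the large losses need a threefold or greater difference that no passage predicts. The document history speaks of events, the reading under which the loss is smaller. Protocol 6.5 also points to Table 6-5, where needing assistance with a low glucose is grade 2, so severe can be read as grade 2. Finally, Period 1 ends at each patient's confirmed failure, so its length may differ by arm, and neither chi-square nor Fisher on crude proportions adjusts for that.

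Much of this stands as a limit on importance. It does not make the condition a suitable one for a chi-square test: intent explains it, but an observed-count threshold still drops tables whose expected counts are adequate. Low expected risk in both arms makes the harmful case unlikely, but an unexpected imbalance is what a safety comparison is for. Unequal Period 1 length affects the test as written equally. The grade 2 reading is reasonable and reduces the severe question to missing detail: whether suspected grade 2 counts, and which glucose limit applies.

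**Conclusion.** The concern holds and is minor. As written, the comparison is withheld whenever one arm has 5 or fewer, including clearly unbalanced tables that meet the usual expected-count criterion. The loss is large (about 37 to 60 percentage points) only when the lower arm is at about 0.5% or below and the ratio is about 3 or more. At a twofold ratio it is 5 to 22 points with the lower arm at 0.2% to 0.5%, about 6 points at 1%, and nil at 2%. These figures assume 1000 per arm, two-sided 0.05 and a patient count; the true rates are illustrative, and the loss is smaller if the 5 counts recurrent events. Descriptive tables by arm and period remain, and the primary conclusion is unaffected. The missing definition of severe is a lesser drafting point that can be settled in the same paragraph.

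**What to change.** Replace the condition in SAP 2.3.5 so that the sentence reads: *The numbers of patients with at least one hypoglycemic event and with at least one severe hypoglycemic event during Period 1 will be compared between treatment approaches in the SAF by chi-square if all expected cell counts are at least 5, and by Fisher's exact test otherwise.* In the same paragraph, state which of the SAP's own categories counts as severe (grade 2 only, grade 2 plus suspected grade 2, or the Severe rating), and reconcile it with protocol 6.5 and Table 6-5. If treatment codes are already open, label the change post hoc, as Addendum 1 does for its other additions.

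The cost is two sentences and a few lines of code. The statistical price is that Fisher is conservative when used. With equal true rates in both arms, the false-positive rate of the combined rule is 0.5% (rate 0.2%), 1.4% (0.3%), 3.1% (0.5%) and about 5% (1% and 2%).
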